8.2.12. Study Drug Exposure

Duration of exposure to study medication will be summarized by treatment groups for the Double-blind Treatment Period as well as for the Open-label Treatment Period.

8.3. Study Periods Relative to Treatment

Definitions of the start and end of the Double-blind and Open-label Treatment Periods and reference visits are presented in [Table 9](#).

Table 9: Duration and Reference Visits for Double-blind Treatment Period and Open-label Treatment Period

Period	Start of period	Reference visit of period	End of period
For efficacy analysis:			
Week 1 – Week 25 (Week 1 – End of Double-blind Treatment Period)	Start date and time of the first IMP infusion	Baseline (before infusion of IMP)	Week 25 (before infusion of IMP)
Week 25 – Week 53 ^b (Week 25 – End Open-label Treatment Period)	Start date and time of the first IMP infusion at Week 25	Baseline (before infusion of IMP)	Week 52
For safety analysis:			
Week 1 – Week 25 (Week 1 – End of Double-blind Treatment Period)	Start date and time of the first IMP infusion	Baseline (before infusion of IMP)	Week 25 (before infusion of IMP)
Week 25 – Week 57 ^b (Week 25 – End of Open-label Treatment Period)	Start date and time of the first IMP infusion at Week 25	Baseline (before infusion of IMP)	Week 57
Week 1- End of Open-label Treatment Period	Start date and time of the first IMP infusion	Baseline (before infusion of IMP)	Week 57

8.3.1. Study Time Periods for Adverse Events

Adverse events (AEs) with onset date/ time after start of first infusion of IMP are TEAEs. Assessment whether an AE is considered treatment-emergent, will take place after imputation of partially missing dates (see Section 8.1.2).

The TEAE analysis will be done for both treatment periods. An AE will be counted for the analysis of a period if the onset of the event falls within the period. For the definition of start and end of the periods see Table 9.

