#### 9.4.7. Safety Analyses

All safety analyses will be performed by treatment group using the Safety Analysis Set. Adverse events will be coded using the Medical Dictionary for Regulatory Activities.

Treatment-emergent AEs (TEAEs) are defined as AEs reported at or after the start of IMP administration. The number and percentage of subjects with TEAEs will be reported. Frequency counts and percentages will also be presented for subjects with treatment-emergent SAEs, TEAEs leading to withdrawal or discontinuation of investigational product, TEAEs by severity, and TEAEs by relationship to investigational product. All AEs will be listed.

Analyses of other safety assessments such as ECGs, vital signs, and clinical laboratory safety markers will be described in the SAP.

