8.1.3. Adverse Events

Imputations in the adverse events dataset are used for slotting events to the appropriate study time periods and for sorting in data listings. They will not be used to calculate duration of adverse events (AEs). If an AE start or end date is missing, then the duration of the AE will be set to missing.

As a rule, the missing start date elements will be imputed with following priorities:

- The event is counted as TEAE for IgPro20 with the earliest onset possible.
- The event is counted as TEAE for placebo with the earliest onset possible.

CONFIDENTIAL

For subjects randomized to Placebo in the Double-blind Treatment Period who have already transitioned to the Open-label Treatment Period, if due to missing elements the event qualifies to either IgPro20 or placebo, the event is assigned to be treatment-emergent in the IgPro20 Open-label Treatment Period.

Table 2: Imputation of Missing Dates for AEs

Date	Missing Element	Rule
Start Date	day, month, and year	
Do not impute completely missing AE start dates.
 
Double-blind Treatment Period
 
 The AE will be deemed treatment-emergent during the Double-blind Treatment Period (Week 1-25) if the AE end date does not indicate that the AE ended prior to IMP start date (Week 1), otherwise, the AE will be deemed not treatment emergent. 
Open-label Treatment Period
 
 The AE will be deemed treatment-emergent during the Open-label Treatment Period (Week 25-53) if the AE end date does not indicate that the AE ended prior to IMP start date (Week 25), else the AE will be deemed treatment-emergent in the Double-blind Treatment Period (Week 1-25) if the AE end date does not indicate that the AE ended prior to IMP start date (Week 1), otherwise, the AE will be deemed not treatment emergent.

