Start Date	day, month only	
Double-blind Treatment Period
 
 If the year of AE start date is the same as the year of IMP start date (Week 1), and the AE end date indicates the AE ended after IMP start date (Week 1), then set AE start date to IMP start date (Week 1), otherwise set AE month and day to January 1st 
Open-label Treatment Period
 
 If the year of AE start date is the same as the year of IMP start date (Week 25), and the AE end date indicates the AE ended after IMP start date (Week 25), and IMP start date (Week 25) is not missing then set AE start date to IMP start date (Week 25), else if the year of AE start date is the same as the year of IMP start date (Week 1), and the AE end date indicates the AE ended after IMP start date (Week 1) then set AE start date to IMP start date (Week 1), otherwise set AE month and day to January 1st
	day only	
Double-blind Treatment Period
 
 If the month/year of AE start date is the same as the month/year of IMP start date (Week 1), and the AE end date indicates the AE ended after IMP start date (Week 1) then set AE start date to IMP start date (Week 1), otherwise set day of AE start date to 1 
Open-label Treatment Period
 
 If the month/year of AE start date is the same as the month/year of IMP start date (Week 25), and the AE end date indicates the AE ended after IMP start date (Week 25), and IMP start date

CONFIDENTIAL

Date	Missing Element	Rule
		(Week 25) is not missing then set AE start date to IMP start date (Week 25), 
else if the month/year of AE start date is the same as the month/year of IMP start date (Week 1), and the AE end date indicates the AE ended after IMP start date (Week 1) then set AE start date to IMP start date (Week 1),
End Date	any date element	No imputation for completely or partially missing AE end dates; as applicable, report the AE as ongoing and the AE duration as missing.

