11.2. Adverse Events

Adverse events will be coded using the Medical Dictionary for Regulatory Activities (MedDRA) version 26.1 or higher. TEAEs are defined as AEs started after the start of the first infusion of IMP. All AEs regardless of when they were reported will be listed.

An AE will be counted in the respective analysis if the onset of the event falls within the period. For the definition of start and end of the periods see [Table 9](#).

- An overview summary of TEAEs, including number of subjects, percentages of subjects, the number of events, including the following:
 - Any TEAE.
 - TEAEs related to IMP.
 - Temporally associated TEAEs (defined as an AE with an onset between the start of the IMP infusion and up to 72 hours after the end of IMP infusion).

- TEAEs leading to permanent discontinuation of IMP.
- TEAEs leading to withdrawal from study.
- TEAEs leading to IMP dose interruptions.
- Serious TEAEs.
- Serious TEAEs related to the IMP.
- Temporally associated serious TEAEs.
- Fatal serious TEAEs.

The following descriptive tables will be generated for TEAEs, including number of subjects, percentages of subjects, and the number of events:

- TEAEs by System Organ Class (SOC) and Preferred Term (PT).
- TEAEs by SOC, PT, and maximum severity (presenting number and percentages of subjects).
- Causally related TEAEs by SOC and PT.
- Temporally associated TEAEs by SOC and PT.
- All AE summaries presented by SOC and preferred term will include a virtual SOC comprising of local reactions, ie, all AEs reported within the MedDRA High level terms “Administration site reactions NEC” or “Infusion site reactions” or “Injection site reactions”. Local reactions will be analyzed by using a virtual SOC called “local adverse events”.

All tables will be displayed in descending order of total incidence by preferred term and by SOC and PT, respectively.

Number of events are counted within the respective period and treatment group.

Temporally associated TEAEs are defined as AEs with an onset between the start of the infusion and up to 72 h after the end of IMP infusion. In case time of onset of AE is missing, the AE is considered temporally related, if the onset of the AE is between the day of the start of infusion and the day of the end of infusion + 3 days (inclusive).

The following listings will be provided:

- All Adverse Events
- All serious TEAEs

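### Read literally, the SAP's treatment-emergent definition excludes the partial-date events that its own imputation rule places on the first-infusion date in order to count them

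*SAP*

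**What the plan says.** Four statements bear on this point.

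- **SAP definition.** Section 8.3.1: "Adverse events (AEs) with onset date/ time after start of first infusion of IMP are TEAEs". Section 11.2: "TEAEs are defined as AEs started after the start of the first infusion of IMP". Neither has an *at or* or *on or*.
- **Order of operations.** SAP 8.3.1 says that the treatment-emergent assessment "will take place after imputation of partially missing dates".
- **Imputation rule.** SAP 8.1.3, Table 2, covers a start date lacking the day, or the day and month. If the known part matches first dosing and the end date shows that the event outlasted first dose, the instruction is "then set AE start date to IMP start date (Week 1". The first listed priority is "The event is counted as TEAE for IgPro20 with the earliest onset possible", followed by the same for placebo.
- **Protocol definition.** Section 9.4.7 takes TEAEs to be "AEs reported at or after the start of IMP administration".

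SAP Section 5, which lists the changes to the planned analyses after early termination, does not mention a change in the TEAE definition. The only rule for a missing onset time is in SAP 11.2. It works at day level and serves to decide whether an event is temporally associated with an infusion.

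**The concern.** The imputation and the definition work against each other. Table 2 moves an uncertain onset to the first-infusion date so that the event will be counted. The definition then asks for an onset after that infusion began, and an onset equal to the boundary does not satisfy *after*.

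The result is also out of order. Under Table 2, an event with no start date at all is deemed treatment-emergent unless its end date shows that it ended before dosing. An event known to have started in the month of first dosing and to have ended after it would fail. More information gives the less cautious classification.

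The stake is the content of the TEAE tables. With early termination, laboratory, vital-sign and ECG data go to SDTM datasets only (SAP 11.4 and 11.5), so the double-blind TEAE tables carry most of the summarized safety information. They should follow one definition, and it should be the protocol's unless a change is declared.

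**Working it through.** The plan gives no figure to reproduce, so the check applies the rules to example records.

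**Inputs.** The definition and order of operations come from SAP 8.3.1 and 11.2, the imputation from SAP Table 2 (day missing, double-blind rule), and the inclusive alternative from protocol 9.4.7. For illustration only, the first infusion is assumed to start on 10 Sep 2024 at 10:00.

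**Step 1, impute.** If month and year match first dosing and the event ended after first dose, onset becomes 10 Sep 2024. Otherwise it becomes the first of the known month.

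**Step 2, test.** Neither section says how a date without a time is to be compared with an infusion start time. Three conventions were tried: (a) date against date; (b) the imputed date taken as 00:00 against 10:00; (c) the imputed onset given the infusion start time.

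| Partial onset | Imputed onset | *after*: a / b / c | *at or after*: a / b / c |
|---|---|---|---|
| Sep 2024, ended 20 Sep | 10 Sep | no / no / no | yes / no / yes |
| Oct 2024, ended 9 Oct | 1 Oct | yes / yes / yes | yes / yes / yes |
| Aug 2024, ended 20 Sep | 1 Aug | no / no / no | no / no / no |
| Sep 2024, no end date | 1 Sep | no / no / no | no / no / no |

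The first row is the conflict. Under the SAP's *after*, the event fails in every convention. Under *at or after* it passes in two of three, failing only where a missing time defaults to midnight. Changing the inequality alone is therefore not enough; a missing-time rule is needed as well.

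The last row is a neighbouring gap. An ongoing event in the month of first dosing does not meet the ended-after condition, falls to the first of the month, and is usually placed before dosing under either definition.

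**Step 3, what is not affected.**
- An onset imputed to the Week 25 IMP start date is later than the Week 1 infusion and passes.
- A wholly missing start date is not imputed but classified directly from the end date.
- A Day 1 reaction with a recorded time after infusion start passes under either wording.

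**Step 4, Day 1 events without a time.** If the first infusion starts at 10:00 and only the date of onset is recorded, whether onset was after 10:00 cannot be determined. SAP 11.2 would class the event as temporally associated by its day-level rule, but gives no corresponding rule for TEAE status.

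**Step 5, size per subject.** SAP Section 3 gives 16 randomized. The actual split is not stated. Assuming 2:1 and all treated, 16 × 2/3 = 10.7, or about 11 on IgPro20. One subject whose only report of a term is an affected event changes that term's incidence by 1/11 = 9.1 points. With 10 or 12 IgPro20 subjects it would be 1/10 = 10.0 or 1/12 = 8.3 points.

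**The case against.** The best reply is that the SAP makes its intent plain. Section 8.1.3 says that these events are to be counted, Table 9 starts the safety period at the moment the first infusion starts, and 11.2 treats temporally associated events as a kind of TEAE. A programmer reading all of this would probably count them. SAP 8.2 also refers full derivation details to separate dataset specifications, which may contain a missing-time rule. The analysis is descriptive, no safety decision depends on the boundary, and all AEs are listed whatever their timing.

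Much of this stands. It shows that the intended result is not in doubt and that no event disappears from the report. It does not remove the conflict. The definition is stated twice without the protocol's *at or*, and is expressly applied to imputed dates. A specification written from that definition would reproduce the exclusion, while one written from 8.1.3 would not.

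Two stronger readings are tempting, and the documents support neither.
- A reader might infer that Day 1 infusion reactions drop out of the TEAE tables. A reaction timed after infusion start remains a TEAE. At least the first infusion of Week 1 is supervised on site (protocol 6.9), and nothing suggests that onset times are often missing.
- A reader might infer that every untimed Day 1 event is excluded, or that incidence is in fact understated. An untimed event is indeterminate under the SAP wording, and no count of affected records is available.

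**Conclusion.** The definition is wrong as written. It departs from the protocol without being listed as a change, and taken literally it defeats the SAP's own imputation priority for partial onsets placed on the Week 1 IMP start date. For Day 1 events with no recorded time the rule is missing, so their status is undefined.

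The scope is narrow: the imputation branch requires a matching partial date and an end date after first dose. The number of affected events is unknown and may be zero. If one occurs in an IgPro20 subject who has no other report of that term, the term's incidence moves by about 9 points, assuming roughly 11 IgPro20 subjects from a 2:1 split of 16. The analysis is descriptive, so the consequence is confined to the accuracy of the TEAE tables.

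**What to change.** In SAP 8.3.1 and 11.2, define a TEAE as an AE with onset at or after the start of the first IMP infusion. This restores the protocol's inclusive boundary and keeps the SAP's reference to onset (the protocol speaks of AEs reported). Add one sentence: an AE whose onset falls on the date of first infusion, with the time missing or the date imputed, is counted as a TEAE. Both parts are needed, because the inequality alone fails where a missing time defaults to midnight.

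The cost is a sentence in two sections and one condition in the program. The downside is that an occasional Day 1 event that began before the infusion, but has no recorded time, will be counted as treatment-emergent; that errs in the conservative direction. The change does not close the gap for ongoing events with a partial onset in the month of first dosing. That needs its own line in Table 2.

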8.3.2. Study Time Periods for Concomitant Medications

The following classification of concomitant medication related to start date and the end date of IMP will be applied. Each medication belongs to one of the following categories:

- Assign to 'Prior' if the medication end date is before the date of the first IMP infusion.
- Assign to 'Concomitant in Double-blind Treatment Period' if the medication start date is at or before start of first IMP infusion at Week 25 or the medication start date

CONFIDENTIAL

is at or before the end of the last IMP infusion in the Double-blind Treatment Period AND the medication end date is at or after start of first IMP infusion at Week 1.

- Assign to 'Concomitant in Open-label Treatment Period' if the medication start date is at or before start of first IMP infusion at Week 53 or the medication start date is at or before the end of the last IMP infusion in the Open-label Treatment Period AND the medication end date is at or after start of first IMP infusion at Week 25.
- Assign to 'Post' if the medication start date is after the date of the last IMP infusion.

If a start or stop date is partially missing, the imputation takes place before the classification of the medication in the categories above.

8.3.3. Study Time Periods for Medical History

Prior medical conditions are those which end before the start of first infusion of IMP. All other Medical History entries are Concomitant medical conditions, including those with missing end date.

8.4. Values of Potential Clinical Importance

Not applicable.

9. STUDY POPULATION

Unless otherwise stated, all tables and listings in this section will be based on the ITT analysis set, and all summaries and data listings will use treatment labels.

9.1. Disposition of Subjects

The following summaries will be provided by treatment group, treatment period and overall:

- Subjects in each of the analysis sets described in Section 6.
- Subject status, including:
 - subjects screened,
 - screen failures (including the reason),
 - subjects randomized,
 - completed IMP,
 - discontinued IMP (including the primary reason)
 - completed the study
 - withdrawals from the study (including the primary reason).

Reasons for study withdrawal and IMP discontinuation will be presented in the order they are displayed in the electronic Case Report Form (eCRF).

CONFIDENTIAL

The following listing will be provided:

- Reasons for study withdrawal including the date of withdrawal.

9.2. Protocol Deviations

The following summaries will be provided by treatment group:

- All major protocol deviations during the Screening or Double-blind Treatment including inclusion and exclusion.

The following listing will be provided:

- All protocol deviations.

9.3. Demographic and Baseline Characteristics

All demographic and Baseline characteristics summaries will be based on the ITT analysis set. They will be presented in summary tables by treatment sequence. Continuous data will be summarized by descriptive statistics and categorical data will be summarized by frequency distributions. Age will be described as both a continuous and a discrete variable. By-subject listings will be provided for demographic and Baseline characteristic data.

The following summaries will be provided by treatment group and overall, for ITT analysis set:

- Demographic characteristics
 - Age (years)
 - Age group (18-19, > 19 years)
 - Sex
 - Ethnicity
 - Race and racial combinations
 - Body weight, baseline assessment (kg)
 - Height (cm)
 - BMI, baseline assessment (kg/m²)
 - Prior IgG treatment (identified by ATC 3 = “IMMUNOGLOBULINS”)
- Disease characteristics at Screening

The following listings will be provided:

- Demographic characteristics
- Disease characteristics at Screening
- Medical history

CONFIDENTIAL

9.4. Prior and Concomitant Medications

Prior and concomitant medications will be coded using WHO Drug Dictionary Enhanced (WHO-DDE) 2022/2023 or more recent version, and listed.

9.5. Non-Pharmacological Interventions and Physiotherapy

Non-pharmacological intervention data and physiotherapy will be provided in the SDTM data sets.

10. EFFICACY

This section describes the planned restricted analyses of efficacy endpoints after the premature discontinuation of the study. The analysis will be done on the ITT analysis set.

10.1. Standardized Standing Test

Efficacy will be assessed using a standardized standing test. The standardized standing test mimics daily activities of POTS in a standardized manner [Finucane et al, 2019], and is therefore considered to be an objective, interpretable, and meaningful measurement to both patients and health care professionals.

In general, subjects are asked to lie supine for 10 minutes to achieve stable baseline blood pressure (BP) values. At the end of the 10 minutes, baseline HR and BP will be assessed. After rest, subjects are asked to stand up as quickly as possible during inspiration (where possible) to minimize straining and arm movement. Heart rate and BP will be assessed at 1, 3, 5, 7 and 10 minutes of standing. Subjects are then asked to sit or lie down until they have recovered. A separate standardized standing test protocol will be provided to sites with more detail on how to perform this assessment.

The standardized standing test will be performed as the last assessment at the time points specified in the Schedule of Activities.

10.2. Primary Estimand and Analysis of Primary Efficacy Endpoint

10.2.1. Detail of Primary Estimand

According to the study protocol, the primary comparison of interest was to quantify the treatment effect of IgPro20 versus placebo. The treatment effect of interest was the difference (IgPro20 vs. placebo) in the proportion of subjects no longer meeting diagnostic criteria of post-COVID POTS as measured by active standing test (no longer experiencing HR increase of ≥ 30 bpm, in the absence of 20 mmHg decrease of SBP [orthostatic hypotension]).

The protocol-defined attributes of the primary estimand, as defined in the ICH E9(R1) guidance, are provided in Table 5 of the CSP. Due to the premature discontinuation of the study the

primary estimand cannot be assessed; only observed data are presented and all analyses are descriptive in nature (see Section 5).

10.2.2. Analysis of Primary Endpoint

The subject's response status of no longer meeting diagnostic criteria of post-COVID POTS as measured by standardized standing test (ie, no longer experiencing HR increase of ≥ 30 bpm, in the absence of 20 mmHg decrease of SBP [orthostatic hypotension]) will be assessed as the primary endpoint.

A subject is considered a responder if,

$$\begin{aligned} \text{HR}_{W25,10\text{min}} - \text{HR}_{W25,0\text{min}} &< 30 \text{ bpm} \text{ and} \\ \text{SBP}_{W25,\text{as}} - \text{SBP}_{W25,\text{bs}} &> -20 \text{ mmHg} \end{aligned}$$

Where, $\text{HR}_{W25,10\text{min}}$ indicates the average of the two highest HR measures (bpm) within 10 minutes after start of the standing test at W25, $\text{HR}_{W25,0\text{min}}$ indicates the heart rate measure (bpm) at start of the standing test at W25, $\text{SBP}_{W25,\text{as}}$ indicates the systolic blood pressure measure (mmHg) at any time point within 10 minutes after start of the standing test at W25, and $\text{SBP}_{W25,\text{bs}}$ indicates the systolic blood pressure measure at the start of the standing test at W25.

consequently, a subject is considered a non-responder if,

$$\begin{aligned} \text{HR}_{W25,10\text{min}} - \text{HR}_{W25,0\text{min}} &\geq 30 \text{ bpm} \text{ or} \\ \text{SBP}_{W25,\text{as}} - \text{SBP}_{W25,\text{bs}} &\leq -20 \text{ mmHg} \end{aligned}$$

Response rates [%] will be determined for placebo and IgPro20.

Due to the premature termination of the study not all randomized subjects completed the Double-blind Treatment Period, thus the assessment of response at Week 25 is not always possible. For that reason, response will be assessed by visit based on the available data at each of the following visits, ie., Week 5, Week 9, Week 13, Week 17, Week 21 and Week 25. The multiple imputation strategies as planned in the study protocol for handling missing data will not be performed (see Section 5). For the following intercurrent events, the composite strategy will be applied, and the subject will be considered non-responder for all visits following the ICE:

Table 10: Definition of response for specific ICEs

Intercurrent Event	Strategy	Description	Imputation details for response
Treatment (IMP) discontinuation due to LoE, related adverse event or lack of compliance	Composite	Discontinuation due to lack of efficacy, related adverse event or lack of compliance will be treated as a failure.	For all visits following ICE: non-responder
Prohibited therapies	Composite	Data after the intake of prohibited medication with a potential effect on the primary endpoint will be treated as failure.	For all visits following ICE: non-responder
Death related to IMP or disease	Composite	Death will be considered as treatment failure.	For all visits following ICE: non-responder

CONFIDENTIAL

All symptoms that have been collected during the standardized standing test will be listed.

